9 STATISTICAL ANALYSES

9.1 Overall testing strategy

9.1.1 Overall testing strategy

A multiple testing strategy is applied for the primary and secondary endpoints. The testing strategy starts with testing the primary endpoint at full alpha, followed hierarchically by a fallback type procedure for the secondary endpoints.

The multiple testing strategy starts with testing the primary endpoint (ARR using confirmed relapses), comparing the investigational treatment (ponesimod 20 mg) with the comparator (teriflunomide 14 mg) at full alpha.

If the primary endpoint null hypothesis is rejected, the alpha will be split evenly (1/3 of alpha) between the following three secondary endpoints using the fallback procedure, allowing for passing on alpha within the fallback procedure as per the following sequence:

- Change from baseline to Week 108 in fatigue-related symptoms as measured by the symptoms domain of the FSIQ–RMS [Fatigue]
- Cumulative number of unique active lesions from baseline to Week 108 [CUALs]
- Time to 12-week CDA from baseline to EOS [12-week CDA]

[figure not shown]
If a secondary endpoint listed as part of the fallback procedure above is successful, the preserved alpha in the sequence is passed along to the next secondary endpoint in the sequence and the summed alpha is used for testing that endpoint. Thus, as sequential tests are successful, the alpha accumulates for the endpoints later in the sequence; these endpoints are then potentially tested with a progressively larger alpha, but always with at least 1/3 of the alpha.

In a last step, the secondary endpoint

- Time to 24-week CDA from baseline to EOS [24-week CDA]
- is tested in a subsequent stage following Time to 12-week CDA with the remaining alpha.

A graphical description of this testing strategy for the primary and secondary endpoints following the approach of Bretz et al. [Bretz 2009] is provided in Figure 2.

Figure 2 Overall testing strategy

ARR = Annualized relapse rate; CDA = Confirmed disability accumulation; CUAL = Cumulative number of combined unique active lesions; H = Hypothesis.

The primary null hypothesis will be tested at a two-sided 1% alpha level, and if rejected the study will be declared to show conclusive evidence of efficacy on the primary endpoint. If the primary null hypothesis can only be rejected at the two-sided 5% alpha level, the study will be declared positive.

The alpha level for the overall testing strategy across primary and secondary endpoints is set at 5%. Multiplicity adjustment as per the testing strategy outlined above will be performed. If the null hypothesis for the primary endpoint is rejected at two-sided alpha of 5% this leads to the example scenarios for alpha allocation for the secondary endpoints detailed as in Table 8.

Any further conducted tests will be considered exploratory.

Table 8 Example scenarios secondary endpoint alpha allocation

Scenario	Endpoint	Proportion of α	p-value for test	Statistically significant
1	Fatigue	1/3	$< 1/3 \alpha$	Yes
	CUALs	2/3	$< 2/3 \alpha$	Yes
	12-week CDA	1	$< \alpha$	Yes
	24-week CDA	1	$< \alpha$	Yes
2	Fatigue	1/3	$> 1/3 \alpha$	No
	CUALs	1/3	$< 1/3 \alpha$	Yes
	12-week CDA	2/3	$< 2/3 \alpha$	Yes
	24-week CDA	2/3	$< 2/3 \alpha$	Yes
3	Fatigue	1/3	$< 1/3 \alpha$	Yes
	CUALs	2/3	$> 2/3 \alpha$	No
	12-week CDA	1/3	$< 1/3 \alpha$	Yes
	24-week CDA	1/3	$< 1/3 \alpha$	Yes
4	Fatigue	1/3	$< 1/3 \alpha$	Yes
	CUALs	2/3	$< 2/3 \alpha$	Yes
	12-week CDA	1	$< \alpha$	No
	24-week CDA	0		
5	Fatigue	1/3	$> 1/3 \alpha$	No
	CUALs	1/3	$> 1/3 \alpha$	No
	12-week CDA	1/3	$< 1/3 \alpha$	Yes
	24-week CDA	1/3	$< 1/3 \alpha$	Yes
6	Fatigue	1/3	$> 1/3 \alpha$	No
	CUALs	1/3	$> 1/3 \alpha$	No
	12-week CDA	1/3	$> 1/3 \alpha$	No
	24-week CDA	0		

Scenarios for secondary endpoint alpha allocation are conditional on rejecting the primary null hypothesis.
 CDA = Confirmed disability accumulation; CUAL = Cumulative number of combined unique active lesions.

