9.7.1.2 Statistical Analysis

The main analysis will be based on the FAS. A mixed effect model repeated measures (MMRM) which includes baseline (FSIQ-RMS SWS_{c Base}) and the two stratification factors, i.e., prior use of DMT (Yes/No), baseline EDSS category (EDSS ≤ 3.5, EDSS > 3.5) as covariates, treatment (fixed effects), visit, treatment by visit interaction, and baseline (FSIQ-RMS SWS_{c Base}) by visit interaction is applied. An unstructured co-variance structure shared across treatment groups will be used to model within patient errors. The Kenwood Roger approximation will be used to estimate denominator degree of freedom and adjusted standard errors. This model assumes that missing data follow the

missing at random assumption. Subjects with at least one available score at a post-baseline visit and at the baseline visit are included in the analysis.

Treatment effects per visit are derived based on (difference in) least-square means with corresponding 95% CIs and p-values derived using the t-distribution. They will be presented in tabular and graphical form.

The main comparison for this secondary endpoint is conducted on the difference in least-square means at Week 108. The corresponding p-value is compared to the local significance level of $1/3 \alpha = 0.05/3$.

The SAS code for this model is as follows (considered “draft” until fully validated at analysis stage):

```
proc mixed data=;  
  class subject treatment visit DMT EDSS;  
  model Chg = Base DMT EDSS treatment visit treatment*visit Base*visit/ noint  
  ddfm=kr;  
  repeated visit / sub = subject type = un;  
  lsmeans Treatment*Visit / pdiff CL OM;  
run;
```

If the normality assumptions seems grossly violated the analysis will be conducted based on a rank ANCOVA of change from baseline to Week 108 using a stratified test [see Section 10.3.3].

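### The secondary testing procedure drops the alpha that 24-week CDA holds once it is rejected; returning that alpha to fatigue and CUAL would cost no endpoint power and keep family-wise error within 5%.

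*SAP*

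**What the plan says.** SAP 9.1.1 sets 5% two-sided for the whole strategy. Once the primary null is rejected, "the alpha will be split evenly (1/3 of alpha) between the following three secondary endpoints using the fallback procedure": fatigue, then CUAL, then 12-week CDA. On success, "the preserved alpha in the sequence is passed along to the next secondary endpoint in the sequence". Time to 24-week CDA starts with no alpha and "is tested in a subsequent stage following Time to 12-week CDA with the remaining alpha". It is described as the last step, no onward transfer is given, and further tests are exploratory.

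Table 8 gives six example scenarios. Its footnote reads "Scenarios for secondary endpoint alpha allocation are conditional on rejecting the primary null hypothesis". In scenario 2, CUAL and both CDA endpoints succeed and 24-week CDA is rejected at 2/3 alpha, yet fatigue stays non-significant on 1/3 alpha. In scenario 3 CUAL stays non-significant on 2/3 alpha. In scenario 5 fatigue and CUAL both stay non-significant on 1/3 alpha each. In scenarios 3 and 5, 24-week CDA is rejected at 1/3 alpha.

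The fatigue sections 9.7.1.1 and 9.7.1.2 fix the fatigue level at 0.05/3, with no provision for a later test at a higher level.

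**The concern.** When 24-week CDA is rejected, the alpha it held is free. The plan lets it lapse even if fatigue or CUAL is still open. The graphical approach that 9.1.1 cites allows an arrow from the last hypothesis back to earlier ones.

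What is at stake is a defined set of results. A fatigue p-value between 0.0167 and 0.05 in scenario 2, or a CUAL p-value between 0.0333 and 0.05 in scenario 3, would be reported as not significant although the same 5% could support the claim. Fatigue, the first endpoint in the sequence, is never tested above 0.0167, however well the other three do.

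**Working it through.** **Inputs.** From SAP 9.1.1: alpha 0.05 two-sided; starting weights 1/3, 1/3, 1/3, 0 for fatigue (F), CUAL (C), 12-week CDA (D12) and 24-week CDA (D24); transitions F to C to D12 to D24, each of weight 1; no exit from D24.

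**1. Reproducing Table 8.** A rejected hypothesis hands its whole weight to the next one.

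- Scenario 1: F 1/3; C 1/3 + 1/3 = 2/3; D12 1/3 + 2/3 = 1; D24 1.
- Scenario 2: F keeps 1/3; C 1/3; D12 1/3 + 1/3 = 2/3; D24 2/3.
- Scenario 3: F 1/3; C keeps 2/3; D12 1/3; D24 1/3.
- Scenario 4: F 1/3; C 2/3; D12 keeps 1; D24 0.
- Scenario 5: F and C keep 1/3 each; D12 1/3; D24 1/3.
- Scenario 6: F, C and D12 keep 1/3 each; D24 0.

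All six allocations match the table.

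**2. Unused alpha** = 1 minus the weight still held by unrejected hypotheses.

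- Scenario 2: 1 − 1/3 = 2/3, or 0.0333.
- Scenario 3: 1 − 2/3 = 1/3, or 0.0167.
- Scenario 5: 1 − (1/3 + 1/3) = 1/3, or 0.0167.

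In scenarios 4 and 6 the unrejected hypotheses hold all of it. In scenario 1 nothing is left to test.

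**3. With a weight-1 arrow from D24 to F.** If F is already rejected, the standard graph update sends the arrow on to C.

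| Scenario | Endpoint | Level in plan | Level with arrow |
|---|---|---|---|
| 2 | F | 0.0167 | (1/3 + 2/3) × 0.05 = 0.05 |
| 3 | C | 0.0333 | (2/3 + 1/3) × 0.05 = 0.05 |
| 5 | F | 0.0167 | (1/3 + 1/3) × 0.05 = 0.0333 |
| 5, if F is then rejected | C | 0.0167 | (1/3 + 2/3) × 0.05 = 0.05 |

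No level changes until D24 has been rejected. Every rejection the plan makes is therefore still made, and both CDA endpoints keep exactly the power they have.

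**4. Error rates.** With all four nulls true, the arrow acts only after a false rejection has already occurred, so the family-wise rate is identical with and without it: 4.98%, 4.37% and 3.46% in simulation at correlations 0, 0.5 and 0.8. With some nulls true and the remaining endpoints certain to be rejected:

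| True nulls | Plan | With arrow |
|---|---|---|
| F only | 0.0167 | 0.05 |
| C only | 0.0333 | 0.05 |
| F and C, independent | 1 − (1 − 0.0167)² = 0.033 | 1 − (1 − 0.0333)(1 − 0.0167) = 0.049 |

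**5. Size of the gain.** The SAP gives no power or correlation for any secondary endpoint, so these are assumptions: fatigue and CUAL at 80% marginal power at two-sided 0.05, pairwise correlation 0.2 to 0.5, and 0.8 between the CDA endpoints. Fatigue as written: 80% power implies a mean z of 1.960 + 0.842 = 2.802; the critical value at 0.0167 is 2.394; power is Φ(2.802 − 2.394) = Φ(0.408), about 66%. Simulated gains in percentage points:

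| Marginal power D12/D24 | Fatigue gain | CUAL gain |
|---|---|---|
| 80%/80%, r = 0.2 | 66.1 to 73.5 = 7.4 | 71.8 to 74.1 = 2.3 |
| 80%/80%, r = 0.5 | 66.0 to 72.4 = 6.4 | 71.1 to 73.1 = 2.0 |
| 50%/40% | 66 to 68–69, about 2–3 | 0.4–0.7 |
| 40%/30% | 1.0–1.8 | 0.2–0.5 |
| 30%/20% | 0.5–1.1 | 0.1–0.3 |

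The first two rows rest on 40,000 trials per setting and the others on 200,000. A repeat of the first row with 20,000 trials gave a CUAL gain of 2.5 points.

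**The case against.** The strongest reply is that nothing here is wrong. The SAP announces a fallback-type procedure, carries it through consistently in 9.1.1, Table 8 and the fatigue sections, and controls the error rate. Citing the graphical approach does not commit it to a graph with a loop. That stands: this is neither a contradiction nor an invalid procedure. It does not make the rule a matter of taste, because the alternative costs no endpoint any power and sometimes rejects more.

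The second reply is that forward-only transfer does buy something. With the other three endpoints succeeding, the chance of a false fatigue claim is about 1.7% as written and 5% with the arrow. This stands and should be weighed openly. The stricter protection lies inside a family already held to 5%, and the SAP does not state it as an aim.

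The third is that the arrow acts only if both CDA endpoints are rejected, against an active comparator. This also stands, and it makes the benefit small if CDA power is low.

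Finally, Figure 2 is not reproduced in the text at hand and Table 8 gives only examples. A return arrow in the figure would, however, contradict Table 8 and the fixed 0.05/3.

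**Conclusion.** The point holds as a loss of efficiency. The plan's rule is valid but uniformly dominated, and it leaves 2/3 of alpha unused in scenario 2 and 1/3 in scenarios 3 and 5.

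A reader might infer that the procedure inflates the type I error. It does not: the family-wise rate is at most 5% as written. A reader might also take a gain of 6 to 7 points for fatigue as the expected benefit. The documents do not support that, since it requires CDA endpoints as well powered as fatigue. Across the assumed CDA powers the gain runs from about 0.5 to 7 points for fatigue and is at most about 2.5 points for CUAL. The dominance and the unused shares follow from the SAP's own rules; only the power figures rest on assumptions.

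**What to change.** Before unblinding:

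- In SAP 9.1.1 and Figure 2, add a transition of weight 1 from 24-week CDA to fatigue, passing on to CUAL if fatigue is already rejected. State that any unrejected secondary hypothesis is re-tested at its updated level.
- In Table 8, show the re-tests: scenario 2, fatigue at alpha; scenario 3, CUAL at alpha; scenario 5, fatigue at 2/3 alpha and, if rejected, CUAL at alpha.
- In the fatigue sections 9.7.1.1 and 9.7.1.2, make 0.05/3 the initial level and refer to 9.1.1 for any re-test.
- Amend the matching protocol text. SAP 4.2 records that protocol version 7 introduced the fallback strategy, so this changes a confirmatory strategy set by amendment.

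The cost is those document changes and a somewhat longer description of the procedure. No data or sample size is affected and no endpoint loses power. The sponsor should accept knowingly that the error rate for a fatigue claim alone can rise to 5%. If it prefers the stricter level for fatigue, the SAP should say that this is intended.

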9.2 General rules for data presentations

This section describes the general rules applied for all data displays, unless otherwise specified in each corresponding section. Standard Guiding Rules and Principles and standard outputs are followed where applicable.

SAS version 9.4 is used for the preparation of all tables, listings and figures. Listings are sorted by treatment group, subject number (includes sorting by country and center) and timing (dates and/or visits as applicable). For analyses performed on multiple analysis sets, only one listing containing all analyzed subjects is presented. Names of outputs have a suffix that indicates the analysis set (e.g., _SAF for Safety set).

Data are listed and summarized using appropriate descriptive statistics:

- Number of non-missing observations, number of missing observations, mean, standard deviation, minimum, Q1, median, Q3, and maximum for continuous variables;
- Number of non-missing observations, and frequency with percentage per category (percentages based on the number of non-missing observations) for categorical endpoints;
- Some continuous variables obtained at scheduled visits are graphically presented utilizing box plots, on a time axis scaled by the target days of nominal visits. The box indicates the interquartile range, a horizontal line within the box indicates the median, and a diamond shape indicates the mean. Whiskers denote minimum and maximum values within the boundary of +/- 1.5 times the size of the interquartile range. Circles indicate outliers from +/- 1.5 times the size of the interquartile range.
- Some continuous variables are graphically presented based on mean change +/- SE on a time axis scaled to the target days of the corresponding visit. The standard error SE is derived as SD/\sqrt{N} .

Example table layouts:

ACT-128800/JNJ-67896153
Analysis set: <Set>

Protocol: AC-058B301<TITLE>

	Ponesimod 20 mg N = XX	Teriflunomide 14 mg N = XX	Total N = xx
<XXX>	XX	XX	XX

Treatment groups are displayed in the order (left to right) of Ponesimod 20 mg, Teriflunomide 14 mg, Total (if applicable). For figures, ponesimod is displayed in red with solid line style and teriflunomide is displayed in black with dashed line style.

9.3 Display of subject disposition, protocol deviations and analysis sets

9.3.1 Subject disposition

The number and percent of subjects in the FAS is summarized by country and site.

The number and percent of subjects screened and re-screened (incl. reasons for screening failure), subjects randomized, subjects completing study as per protocol, subjects treated, and subjects completed treatment per protocol, as well as subjects completing both treatment and study as per protocol are summarized for the SCR. For subjects that failed screening more than once, only the reason of the last failure is reported in the summary table.

All reasons for screening failures are included in the listing. The listing also includes the date of screening / re-screening, an indicator variable ('Yes', 'No') for failed screening attempts, the randomization date, and the number of days from successful screening to randomization.

The number and percent of subjects by reason for premature discontinuation from study is tabulated for the FAS. The number and percent of subjects by reason for premature discontinuation from study treatment is tabulated for the SAF.

Time in study and Time on treatment is presented with an inverse cumulative distribution function by treatment arm, descriptive statistics with cumulative time are displayed on the FAS.

Based on the FAS, the number and percent of subjects randomized under protocol versions 1–3 and 4 or higher are summarized by randomized treatment group. Based on the FAS, the number of subjects with data collected and the time on study (from randomization up to EOS) under protocol version 1–3 and under version 4 or higher are summarized by randomized treatment group by using descriptive statistics for continuous variables, overall and by time on study prior to protocol version 4 and time under study protocol version 4 or higher. Cumulative time on study (from randomization up to EOS) is presented overall, and cumulative time on study (from randomization up to EOS) is presented by time relative to version 4 along with percentage of overall time on study (from randomization up to EOS).

All subjects with unmet eligibility criteria are listed. For subjects re-screened unmet criteria from the initial screening visit are flagged. Subjects randomized with unmet criteria in their last screening attempt are flagged in the listing.

9.3.2 Protocol deviations

All protocol deviations as well as important protocol deviations are summarized by category (first timing, then high-level topic), per treatment group and overall on the FAS.

A listing of all protocol deviations (coded term, reported term) is provided on the SCR.

9.3.3 Analysis sets

The number and percentage of subjects in each analysis set and subjects included in the Per protocol analysis with data up to EOS are summarized in a table, per treatment group and overall.

Reasons for excluding subjects from the PPS, as well as reasons for excluding data from the Per protocol analysis are listed and summarized in a table. The time in study up to per protocol exclusion is summarized descriptively on the FAS.

9.4 Analyses of subject characteristics

9.4.1 Demographics

Demographic characteristics [defined in Section 5.2.1] are summarized using descriptive statistics for continuous and categorical data using the FAS, PPS and DL_{CO} safety set. Tables are presented by treatment group and overall. Demographic characteristics on the FAS will also be summarized by geographical region. All variables are also presented in a subject data listing based on the SCR.

9.4.2 Baseline disease characteristics

Baseline disease characteristics [defined in Section 5.2.2] are summarized using descriptive statistics for continuous and categorical data using the FAS and PPS. Tables are presented by treatment group and overall. Baseline disease characteristics on the FAS will also be summarized by geographical region. All variables are also presented in subject data listings based on the SCR.

9.4.3 Other baseline characteristics

Other baseline disease characteristics [defined in Section 5.2.3] are listed based on the SCR.

9.4.4 Medical history

Previous and concomitant medical histories [defined in Section 5.2.4] are summarized separately, by treatment group and overall, by tabulating the number and percentages of subjects who had/have at least one event and had/have each disease/diagnosis (by system organ class [SOC] and preferred term) using the FAS. SOCs are sorted by descending order of frequency. If the frequencies of SOCs are the same, alphabetical order is used. The same rule applies for preferred terms within SOC.

Complication or Symptoms Associated with MS within the last 24 months prior to the study [defined in Section 5.2.4] are summarized, by treatment group and overall, by tabulating the number and percentages of subjects who had/have at least one event and had/have each complication/symptom (by predefined term sorted by descending order of frequency) separately for previous conditions (not ongoing at screening) and conditions ongoing at screening using the FAS.

All variables including - as applicable - the treatment day relative to study treatment start date of start and end date of diagnosis/disease are presented in a subject data listing based on the SCR.

9.4.5 Previous and concomitant therapies

Number and percentages of subjects having taken at least one treatment are presented by at least one therapy, ATC class and individual preferred term within each ATC class (ATC class level 4). All summaries are tabulated by ATC class, and individual preferred terms within each ATC class, for the FAS, by treatment group and overall. ATC classes

are sorted by descending order of frequency. If the frequencies of ATC class are the same, alphabetical order is used. The same rule applies for preferred terms within ATC class. If the frequencies of ATC class are the same, alphabetical order is used. The same rule applies for preferred terms within ATC class.

The above described frequencies are summarized by treatment group and overall for the following therapies:

- Previous therapies (stopped prior to study treatment start)
- Study concomitant therapies (taken between study treatment start and EOS)
- Treatment concomitant therapies (taken between study treatment start and EOT)
- Therapies taken between study treatment start and EOT + 15 days

All therapies taken are reported in one subject listing with all information collected on the eCRF presented, using flags to mark previous, study concomitant, treatment concomitant as well as ongoing at study treatment start using the screened set.

9.4.5.1 Disease modifying therapies (DMTs) for MS

The following therapies are summarized in the same way as for the previous / concomitant therapies above by treatment group and overall on the FAS:

- Previous DMTs for MS
- Study concomitant DMTs for MS
- Treatment concomitant DMTs for MS
- DMTs for MS started after EOT + 7 days

All DMTs for MS taken are reported in one subject listing using flags to mark previous, study concomitant, treatment concomitant as well as ongoing at study treatment start using the FAS.

9.4.5.2 Concomitant steroid for treatment of relapses

Study concomitant steroids (taken between study treatment start and EOS) are summarized in the same way as concomitant therapies by treatment on the FAS.

Accumulated steroid dose for treatment of relapse (i) up to EOS, and (ii) up to EOT + 7 days is summarized using descriptive statistics by treatment group on the FAS. A listing of corticosteroids for treatment of relapses on the FAS is prepared.

9.4.5.3 Beta blocking agents

Treatment concomitant beta blocking agents (taken between study treatment start and EOT) are summarized in the same way as for treatment concomitant therapies on the FAS. A listing of beta blocking agents on the FAS is prepared.

